4.1.2.2. Neonates (infants)

The Enrolled Set will include all neonates/infants

- born to pregnant women in the enrolled set, and
- Who have a valid ICF signed by the mother/ parent(s) /LAR(s) (as appropriate per local regulations).

4.1.3. Per Protocol Set

4.1.3.1. Pregnant women (mothers)

The maternal PPS will include all pregnant women (mothers) *in the enrolled set who* meet all eligibility criteria up to the time of their censoring, either at study completion or prematurely as drop-out (e.g. withdrawn consent, lost-to-follow-up).

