4.1.3.2. Neonates (infants)

The infant PPS will include all neonates / infants

- *born to pregnant women in the PPS and*
- *who* meet all eligibility criteria up to the time of their censoring, either at study completion or prematurely as drop-out (e.g. withdrawn consent, lost-to-follow-up) who have at least one time point evaluation.

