4.2.3. Elimination from Per-protocol analysis Set (PPS)**4.2.3.1. Maternal excluded subjects**

A subject will be excluded from the maternal PPS analysis under the following conditions. (Brackets indicate the code from the eCRF for the indicated question. For questions where the code is the exact same as the question, only the code in brackets is provided).

Code	Condition under which the code is used
900	Invalid informed consent or fraud data. 
 • Individuals who give written or witnessed/thumb printed informed consent after the study has been explained according to local regulatory requirements. 
 – The informed consent given at screening should either include consent for both the mother's participation and participation of the infant after the infant's birth (if consistent with local regulations/guidelines), or consent for the mother's participation and expressed willingness to consider permitting the infant to take part after the infant has been born (if local regulations/guidelines require parent(s) to provide an additional informed consent after the infant's birth). – Both mother and father should consent if local regulations/guidelines require it.

Code	Condition under which the code is used
	
 Individuals who consent to have cord blood collected at delivery for the purpose of the study.
2010	
Protocol violation (inclusion/exclusion criteria).
 
Inclusion criteria for enrolment:
 
 If maternal subject marked as “No” for the following question in the Eligibility Check screen for maternal subjects [frmELIGIBILITYCHECK]: 
 “Did the subject meet all the entry criteria?” [Eligible]

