5.2. Analysis of primary objectives

The primary objectives analyses will be performed on the PPSs overall and possibly by region or other relevant grouping (the groupings are specific to each analysis). *If there is a difference of 5% or more between the number of participants in the enrolled set and the PPS, primary objectives analyses on the enrolled set will also be performed.*

5.2.1. To determine the frequency of pregnancy outcomes in healthy pregnant women with uncomplicated pregnancies at time of enrollment.

5.2.1.1. Analysis of pregnancy outcomes planned in the protocol.

The number and percentage (with exact 95% CI) of women presenting the following outcomes: live birth, fetal death/stillbirth (antepartum or intrapartum), and elective/therapeutic termination will be reported for each event by presence or absence of congenital anomalies.

5.2.1.2. Additional considerations:

The following analysis will be done on the maternal PPS. The intervals of interest are Visit 1 to Visit 5 (delivery). Details of exact confidence intervals analysis are described in section 9.5.2. All frequencies will be reported overall, by country, and if applicable, by region. For example, if there are few subjects for the events of interest, tables by region will also be presented. Frequencies of pregnancy related events of interest will also be presented by age strata (18-34, 35-39, ≥ 40 years).

The number and percentage (with exact 95% CI) of women presenting the following outcomes will be reported:

- Live birth with no congenital anomalies,
- Live birth with congenital anomalies,
- Fetal death/stillbirth (loss at or after 22 weeks of gestation) with no congenital anomalies,
 - Antepartum stillbirth
 - Intrapartum stillbirth

- Fetal death/still birth (loss at or after 22 weeks of gestation) with congenital anomalies,
 - Antepartum stillbirth
 - Intrapartum stillbirth
- Elective/therapeutic termination with no congenital anomalies,
- Elective/therapeutic termination with congenital anomalies

5.2.2. To determine the frequencies of pregnancy related events of interest in healthy pregnant women with uncomplicated pregnancies from visit 1 through visit 6.

Although pregnancy related events of interest occur within the first 42 days after delivery they may only be detected later, and are to be reported throughout the study

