5.2.2.1. Analysis of pregnancy related events of interest planned in the protocol

The number and percentage (with exact 95% CI) of pregnant women presenting with the following events of interest will be tabulated for each event within appropriate time windows. Missing data may be considered a separate category.

5.2.2.2. Additional Considerations:

This analysis will be done on the maternal PPS. For events of interest that include subcategories, the frequency of the main event of interest and of each event subcategory will be included in the analysis. The overall frequency (derived programmatically) will include mothers who present with at least one of the subcategory events. The intervals of interest are Visit 1 up to 42 days after Visit 5. All events reported during the entire study period will be included in this analysis.

Details of exact confidence intervals analysis are described in section [9.5.2](#).

All frequencies will be reported overall, by country, and if applicable, by region. Frequencies of pregnancy related events of interest will also be presented by age strata (18-34, 35-39, ≥ 40 years). The number and percentage of the following events will be reported:

- Maternal death
- Hypertensive disorders of pregnancy:
 - Gestational hypertension,
 - Pre-eclampsia,
 - Pre-eclampsia with severe features (including eclampsia)
- Antenatal bleeding:
 - Morbidly adherent placenta

- Placental abruption
- Cesarean Scar Pregnancy
- Uterine rupture
- Postpartum hemorrhage
- Fetal growth restriction
- Dysfunctional labor
 - first stage of labor
 - second stage of labor
- Gestational diabetes mellitus,
- Non reassuring fetal status
- Pathways to preterm birth:
 - Premature preterm rupture of membranes,
 - Preterm labor,
 - Provider-initiated preterm birth.
- Chorioamnionitis
- Oligohydramnios
- Polyhydramnios
- Gestational Liver Disease:
 - Intrahepatic Cholestasis of Pregnancy (ICP)
 - Acute Fatty Liver of Pregnancy
- Maternal Sepsis
- Any other pregnancy related event considered by the investigator to be of concern

5.2.3. To determine the frequencies of neonatal events of interest in all neonates live-born to women enrolled in the study.

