5.3.1.2. Additional considerations

This objective will not be performed.

5.3.2. To determine frequencies of pregnancy related events of interest according to GAIA levels of diagnostic certainty (where these are specified) in healthy pregnant women with uncomplicated pregnancies at time of enrolment.

5.3.2.1. Analysis of pregnancy related events of interest planned in the protocol.

To determine the frequencies of pregnancy related events of interest according to GAIA levels of diagnostic certainty (where these are specific) (APPENDIX D of protocol).

Considering all pregnant women followed from enrolment through Visit 6, the number and percentage of subjects with at least one maternal event of interest will be computed by GAIA levels of diagnostic certainty, with exact 95% CIs.

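### The primary frequencies are plain percentages of per-protocol sets that keep drop-outs, with no rule for subjects lost before an event could be observed; with the PPS as N, pregnancy-outcome, delivery, postpartum and later neonatal frequencies read too low

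*SAP*

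**What the plan says.** All references are to SAP Amendment 2.

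- **Maternal set (4.1.3.1).** Women in the enrolled set who meet the eligibility criteria "up to the time of their censoring, either at study completion or prematurely as drop-out (e.g. withdrawn consent, lost-to-follow-up"). Leaving early does not remove a woman.
- **Infant set (4.1.3.2).** The same wording, restricted to infants "who have at least one time point evaluation".
- **Elimination codes (4.2.3).** There are two: code 900 for invalid consent or fraud, and code 2010, headed "Protocol violation (inclusion/exclusion criteria"). Neither concerns incomplete follow-up.
- **Pregnancy outcomes (5.2.1.2).** On the maternal PPS: "The number and percentage (with exact 95% CI) of women presenting the following outcomes will be reported". The outcomes listed have no row for unknown, and no missing-data rule is given.
- **Pregnancy related events (5.2.2).** "This analysis will be done on the maternal PPS", over an interval from Visit 1 to 42 days after Visit 5. On missing data, 5.2.2.1 says only: "Missing data may be considered a separate category".
- **Neonatal events (5.2.3).** Number and percentage on the infant PPS, with the same optional missing category. By definition the events occur in the first 28 days.
- **Missing data (10.1.2).** Covers dates, laboratory results and diary symptoms. It does not cover an outcome that was never observed.

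**The concern.** A woman who withdraws after Visit 1 and before delivery remains in the PPS. She has no Visit 5, so the interval in 5.2.2.2 cannot be completed for her, and nobody sees whether she had a live birth, a stillbirth or a postpartum haemorrhage. If the percentage is taken over the PPS, she adds one to N and nothing to n. The same holds for an infant lost before day 28, for events that could still have arisen.

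According to SAP 2.1, the study is meant to supply background rates for later maternal RSV immunization trials. A background rate that is too low because of incomplete follow-up would make a later trial with better follow-up look worse than it is. By-country tables could also differ because retention differs.

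The SAP handles the same problem properly elsewhere. For the RSV endpoints, 9.5.1 stops person-time at last follow-up, and 5.3.6.2 and 5.3.7.2 plan Kaplan-Meier curves. The primary frequencies have no equivalent.

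**Working it through.** The SAP gives no drop-out rate, expected event rate or sample-size derivation, so there is no figure of its own to reproduce.

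**Inputs**
- From the SAP: N about 2300 women (2.1); Clopper-Pearson intervals for proportions (10.1.5.1).
- Assumed: d (share lost) 5-15%; p (true risk) 0.5-10%; a true live-birth frequency of 99%; r (risk in drop-outs relative to stayers) 0.5-3.

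**Formula.** Let f be the share of the drop-outs' event risk that falls after they leave. With the PPS as N and loss unrelated to risk, the expected frequency is p(1 - d x f), so the relative bias is -d x f.

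**Live birth, f = 1**
- d = 5%: 99% x 0.95 = 94.1%
- d = 10%: 99% x 0.90 = 89.1%

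Normal-approximation half-widths at N = 2300 are 1.96 x sqrt(0.941 x 0.059/2300) = 1.0 point and 1.96 x sqrt(0.891 x 0.109/2300) = 1.3 points. The shortfalls are 4.95 and 9.9 points.

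**A 5% event, f = 1, expected counts**

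| d | PPS as N | Observed women as N |
|---|---|---|
| 5% | 109/2300 = 4.74% (3.91-5.69) | 109/2185 = 4.99% (4.11-5.99) |
| 10% | 104/2300 = 4.52% (3.71-5.45) | 104/2070 = 5.02% (4.12-6.05) |
| 15% | 98/2300 = 4.26% (3.47-5.17) | 98/1955 = 5.01% (4.09-6.08) |

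**Bias against precision, d = 10%, f = 1**

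| True p | Bias (points) | 95% CI half-width (points) |
|---|---|---|
| 0.5% | -0.05 | 0.29 |
| 2% | -0.20 | 0.56 |
| 5% | -0.50 | 0.87 |
| 10% | -1.00 | 1.19 |

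**Partial exposure, d = 10%.** The relative bias is -5% at f = 0.5, -2.5% at f = 0.25, and 0 for an event already settled when the subject leaves.

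**Informative loss, d = 10%, f = 1.** The relative bias is (1-d)/(1-d+d x r) - 1: -5.3% at r = 0.5, -18.2% at r = 2 and -25.0% at r = 3. With observed subjects as N it is 1/(1-d+d x r) - 1: +5.3% at r = 0.5 and -9.1% at r = 2.

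**Do other provisions of the SAP correct this?**
- *Missing category.* It is optional, sets no denominator and is absent for pregnancy outcomes. Where the SAP does fix one (demography, 5.1.1), percentages are of total subjects, so missing subjects stay in N.
- *5% rule in 5.2.* It compares the enrolled set with the PPS. Drop-outs are in both, so they neither trigger the extra analysis nor are removed by it.
- *Sensitivity analysis in section 8.* It concerns source-data verification thresholds, not follow-up.

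**The case against.** **The SAP does not say that drop-outs count as event-free.** This stands. A reader might infer it, but it is only the default consequence of a number and percentage on the PPS. Table-level denominators may be fixed in the table shells that 10.2 files elsewhere. The SAP text itself sets no other denominator.

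**The bias need not equal the drop-out share.** This also stands. Equality needs every drop-out to leave before the window and loss to be unrelated to risk. Women enrol in the third trimester, and hypertensive disorders, gestational diabetes or oligohydramnios can be diagnosed before a woman leaves, so f can be below 1.

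**Not all neonatal events are exposed.** Correct. The infant set requires one evaluation, and size for gestational age, birth weight, macrosomia and preterm birth are settled at birth. Neonatal death, infections and failure to thrive remain exposed.

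**A contradiction in the GAIA analysis.** A reader might infer one, because 5.3.2.1 begins "Considering all pregnant women followed from enrolment through Visit 6" while 5.3.2.2 uses the maternal PPS. The documents do not establish it: section 5 explains that the first text reproduces the protocol and the second adds detail. The two can be read together, or the phrase may only describe the observation period.

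**The confidence interval.** It would be wrong to say that the interval generally misses the truth. All three PPS intervals for the 5% event contain 5%. At p = 10% and d = 15%, 196/2300 = 8.52% (7.41-9.74) does not contain 10%, and live birth is clearly missed. The bias is systematic either way.

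**Countries with more drop-out would look safer.** This is possible, but the SAP has no country-level retention data to support it.

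**Conclusion.** The point holds in this form: both PPSs keep drop-outs, the primary frequencies are uncensored percentages on those sets, and no rule deals with subjects lost before an event could be observed. With the PPS as N, the frequencies of pregnancy outcomes, labour and delivery events, postpartum events and neonatal events arising after birth are biased downward by about d x f in relative terms.

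That size assumes non-informative loss, and d is itself an assumption. For most single events the bias is smaller than the interval half-width at N = 2300. Live birth is the exception, because its shortfall is several times the half-width and would leave a visible share of women in no outcome category. Events settled at birth or before loss are little affected. The SAP should be amended, since the change is cheap and these rates are the study's primary output.

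**What to change.** - **5.2.1.2:** use women with a known pregnancy outcome as the denominator.
- **5.2.2.2 and 5.3.2.2, labour and delivery events:** use women whose delivery was observed.
- **Postpartum events to day 42, and neonatal events arising after birth to day 28:** report cumulative incidence from delivery or birth, censored at last contact, with death as a competing event where relevant. This matches the censoring already planned for the RSV endpoints.
- **All tables:** show the number lost before each window, and keep the all-PPS percentage as a sensitivity row.

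One tempting shortcut should be avoided: a denominator of subjects with complete follow-up plus any drop-out who had the event. It adds back only drop-outs with events and biases upward. If the true risk is 6.0%, all events occur at or near delivery, and 10% of the remaining women leave before day 42, it gives 0.06/(0.06 + 0.94 x 0.90) = 6.6%, whereas the full PPS would give the correct 6.0%.

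The cost is SAP wording and follow-up flags derived from existing dates. Denominators become slightly smaller and intervals slightly wider. Cumulative incidence needs event dates and its own interval method in place of the exact binomial. Bias from informative drop-out is not removed: at d = 10% and r = 2, an observed-only denominator is still 9.1% too low.

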4.1.3.2. Neonates (infants)

The infant PPS will include all neonates / infants

- *born to pregnant women in the PPS and*
- *who* meet all eligibility criteria up to the time of their censoring, either at study completion or prematurely as drop-out (e.g. withdrawn consent, lost-to-follow-up) who have at least one time point evaluation.

4.2. Criteria for eliminating data from Analysis Sets

Elimination codes are used to identify subjects to be eliminated from analysis. Detail is provided below for each set.

4.2.1. Elimination from Maternal Exposed Set (ES)

Code 900 (invalid informed consent or fraudulent data) will be used for identifying pregnant women (mothers) eliminated from maternal ES.

4.2.2. Elimination from Infant Exposed Set (ES)

N/A

4.2.3. Elimination from Per-protocol analysis Set (PPS)**4.2.3.1. Maternal excluded subjects**

A subject will be excluded from the maternal PPS analysis under the following conditions. (Brackets indicate the code from the eCRF for the indicated question. For questions where the code is the exact same as the question, only the code in brackets is provided).

Code	Condition under which the code is used
900	Invalid informed consent or fraud data. 
 • Individuals who give written or witnessed/thumb printed informed consent after the study has been explained according to local regulatory requirements. 
 – The informed consent given at screening should either include consent for both the mother's participation and participation of the infant after the infant's birth (if consistent with local regulations/guidelines), or consent for the mother's participation and expressed willingness to consider permitting the infant to take part after the infant has been born (if local regulations/guidelines require parent(s) to provide an additional informed consent after the infant's birth). – Both mother and father should consent if local regulations/guidelines require it.

Code	Condition under which the code is used
	
 Individuals who consent to have cord blood collected at delivery for the purpose of the study.
2010	
Protocol violation (inclusion/exclusion criteria).
 
Inclusion criteria for enrolment:
 
 If maternal subject marked as “No” for the following question in the Eligibility Check screen for maternal subjects [frmELIGIBILITYCHECK]: 
 “Did the subject meet all the entry criteria?” [Eligible]

4.2.3.2. Infant Excluded Subjects

A subject will be excluded from the infant PPS analysis under the following conditions

Code	Condition under which the code is used
900	
Invalid informed consent or fraud data.
 
 Infants who were in utero at the time maternal (and paternal, if required) informed consent was given, and who are live-born. If local law requires it: Written or witnessed/thumb printed informed consent for study participation of the infant obtained from parent(s)/LAR(s) within 10 days of birth.
2010	
Protocol violation (inclusion/exclusion criteria)
 
Inclusion criteria for enrolment:
 
 If infant marked as “No” for the following question in the ELIGIBILITY CHECK_NB screen [frmELIGIBILITYCHECK_NB]: 
 Did the subject meet all the entry criteria? [Eligible]

5. STATISTICAL ANALYSES

Note that data derivation rules and statistical methods are described in sections [9](#) and [10.1](#) and will not be repeated below.

The statistical analyses for each objective is divided into two sections. The first section presents the analysis plan exactly as it is written in the protocol. The second section, additional considerations, provides more details of the analysis including any changes that have been made to the analysis plan since the protocol. These changes from the planned analysis in the protocol will also be explained in section [8](#).

5.1. Demography

5.1.1. Analysis of demographics/baseline characteristics planned in the protocol

For the maternal PPS, analyses of demographic and baseline characteristics at Visit 1 will be described.

For the infant PPS, analyses of demographic characteristics at Visit 1-NB will be described. Analyses of lifestyle characteristics will be described at Visit 2 NB.

For Screening Failures, reasons for non-eligibility will be described.

Continuous variables will be summarized by providing the number of observations, mean, 95% confidence interval (CI), standard deviation (SD), median, and range. Categorical variables will be summarized by tabulating counts (N) and the percentage (%) of total subjects having the given characteristics, with missing data considered a separate category.

5.1.2. Additional Considerations

For all the descriptive analyses mentioned above, separate tables will be provided for mother and infant cohorts. The results will be summarized overall and by country.

For the maternal and infants exposed sets, only descriptive statistics for baseline characteristics (ex: age) will be provided because it is a requirement for clinicaltrials.gov. Descriptive statistics for all demographic and baseline characteristics will be provided for the maternal and infant PPS.

In addition to demographic and baseline characteristic mentioned in section [5.1.1](#), we will also provide descriptive statistics of lifestyle characteristics for the mother PPS. These include:

- Highest education level of the mother
- Household environment
- Household composition

- Mother smoking during current pregnancy
- Mother passive smoking exposure during current pregnancy
- Mother consuming alcohol during current pregnancy
- Method of cooking used during current pregnancy
- Mosquito control during current pregnancy
- Would subject have agreed to take part in a vaccine trial during this pregnancy

5.2. Analysis of primary objectives

The primary objectives analyses will be performed on the PPSs overall and possibly by region or other relevant grouping (the groupings are specific to each analysis). *If there is a difference of 5% or more between the number of participants in the enrolled set and the PPS, primary objectives analyses on the enrolled set will also be performed.*

5.2.1. To determine the frequency of pregnancy outcomes in healthy pregnant women with uncomplicated pregnancies at time of enrollment.

5.2.1.1. Analysis of pregnancy outcomes planned in the protocol.

The number and percentage (with exact 95% CI) of women presenting the following outcomes: live birth, fetal death/stillbirth (antepartum or intrapartum), and elective/therapeutic termination will be reported for each event by presence or absence of congenital anomalies.

5.2.1.2. Additional considerations:

The following analysis will be done on the maternal PPS. The intervals of interest are Visit 1 to Visit 5 (delivery). Details of exact confidence intervals analysis are described in section 9.5.2. All frequencies will be reported overall, by country, and if applicable, by region. For example, if there are few subjects for the events of interest, tables by region will also be presented. Frequencies of pregnancy related events of interest will also be presented by age strata (18-34, 35-39, ≥ 40 years).

The number and percentage (with exact 95% CI) of women presenting the following outcomes will be reported:

- Live birth with no congenital anomalies,
- Live birth with congenital anomalies,
- Fetal death/stillbirth (loss at or after 22 weeks of gestation) with no congenital anomalies,
 - Antepartum stillbirth
 - Intrapartum stillbirth

- Fetal death/still birth (loss at or after 22 weeks of gestation) with congenital anomalies,
 - Antepartum stillbirth
 - Intrapartum stillbirth
- Elective/therapeutic termination with no congenital anomalies,
- Elective/therapeutic termination with congenital anomalies

5.2.2. To determine the frequencies of pregnancy related events of interest in healthy pregnant women with uncomplicated pregnancies from visit 1 through visit 6.

Although pregnancy related events of interest occur within the first 42 days after delivery they may only be detected later, and are to be reported throughout the study

